1. SUMMARY

The nutritional status and weight gain trajectories of women during pregnancy influence birth outcomes, health, and the long-term risk for chronic disease for both the mother and child. In 2015, more than one in eight women in the U.S. lived in poverty and women with low incomes are the most vulnerable to poor energy-dense nutrition, sedentary behavior, excess gestational weight gain (GWG) and poor birth outcomes. There is a critical need for scalable and effective healthcare services targeting these under-served, minority women through community-based lifestyle interventions. Especially lifestyle interventions during pregnancy positioned to reduce excess gestational weight gain may reduce risk factors for chronic disease in women and obesity in children. The USDA Special Supplemental Nutrition Program for Women, Infants, and Children (WIC) – a National program – is highly suited to deliver scalable lifestyle interventions in low income and nutritionally at risk pregnant women. However, for the specific population, there is a dearth of clinical trials testing efficacious, well-designed, culturally relevant and appropriately powered interventions aimed to promote healthy weight gain.

Smartphone use is highly prevalent in low income populations and allows for delivery of intensive, theoretically supported behavior change interventions. Moreover, *e*-Health interventions overturn many of the reported barriers for intervention adherence and completion. Therefore, the overarching goal of this research is to adapt an innovative smartphone-based, patient-centered, pragmatic and scalable intensive lifestyle intervention called 'SmartMoms[®]', previously shown to foster appropriate gestational weight gain according to Institute of Medicine (IOM) guidelines [1], for dissemination to pregnant women served by WIC.

In Phase 1 of the current study, SmartMoms[®] will be adapted for low-income women, taking into account cultural sensitivities and an appropriate level of health literacy, using formative research (qualitative survey of 614 WIC clients and staff, structured interviews with WIC mothers) and systematic consultations with a Community Advisory Board and a WIC Peer Advisory Group. As the IRB has determined that phase 1 is not defined as "human subjects research", phase 1 is not included in the current protocol (please see 'Not Human Subjects Research Determination' letter, July 19th 2018). In the proposed phase 2, we aim to test the effectiveness of SmartMoms[®] in a state-wide, randomized controlled trial in 432 low-income women enrolled in the Louisiana WIC program. We hypothesize that, compared to WIC patients receiving usual care, participants receiving SmartMoms[®] will have a greater adherence to the 2009 IOM gestational weight gain guidelines and significant improvements in physiological and behavioral factors.

2. STUDY AIMS

This proposed study 'SmartMoms[®] in WIC', will test the overarching hypothesis that compared to WIC participants receiving usual care, participants receiving SmartMoms[®] will have greater adherence to the 2009 IOM gestational weight gain guidelines and significant improvements in physiological and behavioral factors. The primary aim of the study is to test the efficacy of SmartMoms[®] for improving the incidence of appropriate gestational weight gain (GWG) in a multi-site randomized controlled trial within the Louisiana WIC program that randomizes 432 pregnant women (N=144 normal weight, N=144 overweight, N=144 obese) to either SmartMoms[®] or Usual Care.

2.1. Hypotheses

Relative to WIC participants receiving Usual Care, participants receiving SmartMoms® will have a:

A: higher incidence of appropriate GWG according to the 2009 IOM guidelines

B: smaller deviation in GWG per week from the 2009 IOM guidelines

C: significant improvements in both physiological and behavioral factors including diet quality, physical activity, birth outcomes, postpartum weight loss, quality of life and mood and WIC food voucher redemption rates.

2.2. Endpoints

Primary endpoint:

• Incidence of appropriate weight gain in pregnancy as defined by the 2009 IOM Guidelines [2].

Secondary endpoints:

- Rate of GWG per week
- Maternal diet (24h recall)
- Physical activity (Accelerometry, Pregnancy Physical Activity Questionnaire)
- Quality of life and stress (Depression Anxiety Stress Scales-21, Quality of Life Inventory, Household Chaos Questionnaire)
- Maternal and infant birth outcomes
- Infant feeding style (Infant Feeding Style questionnaire and Breastfeeding Questionnaire)
- WIC food voucher redemption rate
- Postpartum weight retention (measured 1, 6 and 12 months after delivery)

Exploratory endpoints: This study is also powered for a comparison of GWG between BMI categories. As an exploratory aim we will test whether maternal body mass index (BMI) is a moderator of intervention effects on GWG (relative to Usual Care).

Planned post-hoc analyses include testing moderators of intervention effects on GWG in BMI categories, race/ethnicity groups and in the SmartMoms[®] group only, intervention adherence.

3. BACKGROUND AND SIGNIFICANCE

Pregnancy is critical nutritional time point that influences the immediate and long-term health of both mother and child. While the health and nutritional status of women (eg. obesity, smoking etc.) prior to pregnancy is arguably the most important for long-term health outcomes [3], the nutritional status of women during pregnancy including GWG influences birth outcomes, maternal and infant health, and long-term risk for chronic disease in the mother and child [4]. Lifestyle interventions during pregnancy that aim to foster healthy GWG [5-7] may lower the risk of adverse birth outcomes and maternal [8] and childhood [9, 10] obesity. Women who are economically disadvantaged are the most vulnerable to maternal obesity [11, 12], excess weight gain in pregnancy [13, 14] and poor birth outcomes [15-18]. According to the U.S. Census Bureau, in 2015 more than one in eight women and one in four children in the U.S. lived in poverty [19]. Therefore to positively impact the health of the most vulnerable populations' to the effects of obesity there is a critical need for scalable and effective healthcare services that target GWG. The federally-funded program WIC has an unprecedented position to deliver scalable and effective lifestyle interventions in low income and nutritionally at risk pregnant women. According to CDC Pregnancy Risk Assessment Monitoring System data reports that span more than 15 years, at least 50% of the pregnant women supported by WIC are overweight or obese [20] and only 30% achieve appropriate GWG [21]. Moreover because WIC has an established national framework and supports approximately 15% of pregnancies in the US each year [22], WIC has a unique opportunity to disseminate a weight management program to millions of pregnant women.

"e-Health" weight management interventions deliver treatment to people who face barriers to traditional clinicbased treatments and include the use of smartphones. Studies have shown that internet interventions that include counselor support and individualized recommendations produce clinically significant weight loss [23-26] with effect sizes similar to intensive lifestyle interventions delivered in-person [27]. With smartphones, people are "mobile" and less reliant on computers for Internet access [28]. This is significant since 77% of adults in the U.S. own a smartphone [29] and low-income households are the most likely to rely solely on mobile devices for internet access [30]. Smartphones include built-in sensors and paired devices that collect and transmit objective data such as body weight or activity in real-time. They also provide several methods that allow for delivery of near real-time feedback about behavior [31] which is important since behavior change theories, such as learning theory [32], postulates that temporally contiguous, data-driven feedback results in superior behavior change. Smartphones allow for intervention delivery to be intensive and personalized to the needs and adherence of individuals through its varied multimedia functions and access to social media applications. This clearly indicates that smartphone-based interventions should easily reach under-served individuals with limited access to financial and healthcare resources, including the delivery of weight management programs via smartphones in pregnant women. However, there is a dearth of clinical trials testing efficacious, well-designed, culturally relevant and appropriately powered interventions aimed to promote healthy GWG in economically disadvantaged pregnant women. Intensive lifestyle interventions targeting pregnancy weight gain [33-35] or postpartum weight loss [36, 37] in economically disadvantaged women, have been met with poor success. Collectively these trials cite the inherent difficulties of engaging a population that is challenged to meet the basic needs of life which result in low levels of intervention adherence and poor retention rates [37-41]. Thus, there is a clear need for culturally relevant and health literacy appropriate interventions for pregnant women who face disadvantages in financial and healthcare support. Capitalizing on the unprecedented access of WIC to an economically disadvantaged and health disparate population, the overarching goal of this research is to adapt the innovative, smartphone-based, patient-centered, pragmatic and scalable weight management intervention SmartMoms[®], shown to foster healthy GWG, for dissemination to pregnant women served by WIC. If SmartMoms® is efficacious when embedded in the Louisiana WIC program, it will provide the first indication that WIC services could be expanded to meet an important public health need and serve as a conduit for delivering a scalable intervention to pregnant women across the country. Furthermore, given the long-term follow-up of children in the WIC program, this study also provides the framework for future investigations into the effects of prenatal obesity (BMI), GWG and lifestyle interventions on health outcomes in children.

4. RESEARCH DESIGN

This is a multi-site randomized controlled trial, testing the effectiveness of the smartphone-based behavior modification program 'SmartMoms[®]' in pregnant women within the Louisiana WIC program. Equal number of participants will be randomized to either the intervention (SmartMoms) or the control condition (Usual Care). Although the SmartMoms[®] intervention itself lasts 24 weeks (only during pregnancy), women will be enrolled in this study for approximately 18 months; from the 10-16th week of pregnancy until 12 month postpartum follow-up. Study outcomes will be assessed at three time points during pregnancy (early, mid and late, see Table 3) and three visits postpartum (1, 6 and 12 months).

5. STUDY POPULATION

5.1. Participants

The target population is 432 healthy pregnant women certified to receive WIC services during the current pregnancy, who will be will be enrolled from WIC clinics in the 9 WIC regions across Louisiana. Participants will be randomized to either:

- Intervention: SmartMoms (n=216)
- Control: Usual Care (n=216)

An equal number of women in each group (n=72) will be normal weight (BMI 18.5-24.9 kg/m²), overweight (BMI 25.0-29.9 kg/m²) and obese (BMI 30.0 - 40.0 kg/m²).

5.2. Inclusion Criteria

• Pregnant female less than 16 weeks gestation at S1

- 18-40 years of age
- BMI between 18.5 -40 kg/m² using weight measured at the prenatal WIC certification visit
- Expecting a singleton pregnancy
- Certified to receive WIC services during the current pregnancy
- Has Smartphone with internet access
- Willing to be identifiable to other study participants in this study program

5.3. Exclusion Criteria

- Smoking
- Drug or alcohol use
- Non-pregnancy related illness (HIV, cancer, heart disease, type 1 or type 2 diabetes)
- Hypertension (SBP >160 mmHg or DBP >110 mmHg) at S1
- Current mental health issue or eating disorder
- Inability to complete a behavioral run-in task
- Plans to move out of the state in the next 18 months

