9. ASSESSMENT SCHEDULE AND PROCEDURES

The planned schedule of procedures is shown in Table 3. Following the initial screening visit, there are 3 visits in pregnancy (early, mid and late) and 3 visits postpartum (1, 6 and 12 months). Study visits will be conducted at participating WIC clinics. Visits may also be performed at participants' homes, medical care provider offices, or other locations to maximize the opportunity of data collection for women who report difficulty in returning to the clinic. To assist with clinic visit retention, intervention staff will reach out to participants through contact outlets (e.g. telephone call, text message, Facebook group message, video conference) to remind them of upcoming clinic visits throughout the study for both the SmartMoms (Healthy Beginnings) and the Usual Care groups.

Table 3. Schedule of Procedures								
	Pregnancy					Postpartum		
		V1 Screening Early		V2 V3	V4	V5	V6	
	Screening			Mid	Late	1 month	6 months	12 months
(Weeks of gestation)	<16,0	10,0-16,6		24,0-27,6	35,0-37,6	+2,0-6,6	+22,0-25,6	+48,0-56,6
Height	X							
Weight	X	X]	X	X	X	X	X
% Fat by BIA	X	X]	X	X	X	X	X
Behavioral Run in	X]_					
			ATION					
			AI					
Blood pressure	X	X	712	X	X	X	X	X
Questionnaires		Х	ŏ		Х	X	X	X
24h diet recall	X		RANDOMIZ		X		X	X
			2					
Physical activity	X				X		X	X
(5-7 days accelerometry)								
WIC Data Abstraction					X			X
Birth Certificate Data Abstraction						X		

9.1. Visit 1

Participants will have their weight, % body fat, and blood pressure measured. Questionnaires will also be administered. After reviewing the behavioral requirements for each group with study staff, participants will be randomized to either the SmartMoms or Usual Care group. Participants will be provided with a prenatal vitamin to be taken throughout their pregnancy.

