11.2.3. Additional Safety Monitoring

Additional safety monitoring is included in this study. Identification of the following would generate a safety alert and require specific action if noted during any study visit:

- Contraindications to moderate to high intensity physical activity during pregnancy
 - Incompetent cervix/cerclage
 - Persistent 2nd or 3rd trimester bleeding
 - Placenta previa after 26 weeks' gestation
 - Premature labor that requires hospitalization and treatment with medications to stop contractions
 - Ruptured membranes
 - Preeclampsia / gestational hypertension
 - Severe anemia defined as a hemoglobin < 8 or hematocrit < 24

****If any of these conditions are reported, study staff will notify the PI and interventionist(s) that the participant has developed a contraindication to moderate- to high-intensity physical activity in pregnancy. The physical activity component(s) of the intervention may need to be modified. The presence of any of the conditions may not

require a change in any dietary component(s) of the intervention. Participants for whom a change to intervention component(s) is indicated should not be considered withdrawn from the study.

- High blood pressure
 - If measured blood pressure is ≥ 160/110, i.e. systolic blood pressure ≥ 160 mm Hg and/or diastolic blood pressure ≥ 110 mm Hg, study staff will consult with the study MI or his designee. Staff will contact the participant's provider as recommended by the study MI.
 - o If measured blood pressure is ≥ 140/90, i.e. systolic blood pressure ≥ 140 mm Hg and/or diastolic blood pressure ≥ 90 mm Hg, study staff will instruct participants to contact their provider regarding the elevated measure to arrange appropriate follow-up. Additionally, study staff will consult with the study MI or his designee to arrange follow-up as appropriate.
 - At least one blood pressure reading must meet criteria when two readings are taken, and at least two blood pressure readings must meet criteria when three readings are taken.
- Weight loss during pregnancy after randomization All participants
 For all participants, weight safety alert values will be obtained from the weight measured at the clinic visit.
 - For women who are normal weight at enrollment, alert values will be any weight loss from enrollment weight.
 - For women who are overweight at enrollment, alert values will be weight loss of 4% or greater of enrollment weight.

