2.1 Study Sample

At least 330 pregnant individuals certified to receive WIC services during the current pregnancy (had to be certified by October 31, 2023) will be enrolled from WIC clinics across the nine Louisiana Department of Health (LDH) regions.

Eligible participants will satisfy the following inclusion criteria:

1) Aged 18-40 year,

- 2) BMI 18.5-40.0 kg/m²,
- 3) Expecting a singleton pregnancy,
- 4) No current mental health issue or eating disorder,
- 5) Not planning to move out of the area in the next 18 months.

Participants will be excluded for:

- 1) History of or current smoking, drug or alcohol use,
- 2) Significant non-pregnancy related illness (HIV, cancer, heart disease, diabetes),
- 3) Inability to complete the behavioral run-in task.

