Information will be abstracted from the LEERS records on adverse perinatal outcomes, including on the diagnosis of gestational diabetes, gestational hypertension/preeclampsia, and medically indicated Cesarean section (maternal outcomes) as well as neonatal intensive care unit admission and birth weight that will allow for calculation of small for gestational age or large for gestational age (neonatal outcomes). Specifically, we will define medically indicated Cesarean section as deliveries via Cesarean method of delivery with attempt of labor or if prior to 39 weeks with any medical indication. Small for gestational age (SGA, <10th percentile) and large for gestational age (LGA, >90th percentile) will be defined using birth weight for gestations greater than 19 weeks and less than 45 weeks based on the Alexander criteria specific for neonatal sex and rate. Preterm birth will be defined as any birth occurring prior to 37 weeks gestation; the calculation of gestational age at delivery will be determined as the difference in days between delivery date and the estimated date of conception divided by 7, with the delivery date abstracted from the birth certificate record and the date of conception calculated as 280 days prior to the participant self-reported due date.

From these outcomes, a maternal and neonatal composite will be calculated. Specifically, for each participant, the number of adverse maternal outcomes (as listed above) will be summed; from this, a binary maternal composite will be derived with any participant who has a non-zero sum indicated as having a maternal adverse outcome and those with a zero-sum having no maternal adverse outcome. A neonatal composite will be derived analogously based on the adverse neonatal outcomes (as listed above). Other study measures (e.g., baseline characteristics) are briefly defined below.

Gestational age at randomization in weeks is defined as the number of days since the date of conception divided by 7, with the date of conception calculated as 280 days prior to the participant self-reported due date.

Parity is defined categorically as either nulliparous or non-nulliparous based on participant self-report.

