These outcomes will be analyzed analogously to the categorical outcome of study observed GWG per week attainment using a general linear model with a fixed effect for group (SmartMoms®, Usual Care) with a binary distribution and a log odd link function modeling the incidence rates, as well as BMI category (normal weight, overweight, obesity) at randomization, parity (nulliparous, non-nulliparous), and gestational age at randomization as covariates.

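### Women at 140–160 systolic or 90–110 diastolic at screening can be randomized, but the exploratory hypertension and maternal-composite models leave out entry blood pressure: a little power lost and no clear new-onset reading, but no bias

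*Protocol*

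**What the plan says.** **Entry.** The blood-pressure exclusion in Protocol 5.3 is "Hypertension (SBP >160 mmHg or DBP >110 mmHg) at S1". The shorter criteria list in SAP 2.1 has no blood-pressure item; its illness exclusion reads "Significant non-pregnancy related illness (HIV, cancer, heart disease, diabetes".

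**The protocol's own threshold.** Protocol 11.2.3 has a high-blood-pressure safety alert with a lower tier that begins "If measured blood pressure is ≥ 140/90".

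**Measurement.** Table 3 of the Protocol shows blood pressure at screening and at V1. Section 9.1 says of Visit 1: "Participants will have their weight, % body fat, and blood pressure measured". Randomization follows Visit 1 (Protocol 8).

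**Outcome.** SAP 4.2 takes perinatal outcomes from state birth records. The maternal ones are the "diagnosis of gestational diabetes, gestational hypertension/preeclampsia, and medically indicated Cesarean section (maternal outcomes". Any one of them is enough for the composite: "a binary maternal composite will be derived with any participant who has a non-zero sum indicated as having a maternal adverse outcome".

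**Model.** The exploratory part of SAP 4.3 uses a logistic model with group, BMI category, "parity (nulliparous, non-nulliparous), and gestational age at randomization as covariates". SAP 3.3 lists the same three covariates. Randomization is stratified by region and BMI category (SAP 2.2), not by blood pressure.

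**Status.** SAP 1.5 classes pregnancy and birth outcomes as exploratory. SAP 3 says that secondary and exploratory results are not to support definitive conclusions.

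**The concern.** A woman at, say, 150/95 before 16 weeks is high by the protocol's own monitoring rule, yet eligible. If her birth record later shows gestational hypertension or preeclampsia, the analysis cannot tell whether this arose after randomization. The plan already holds two pre-randomization readings that would help and uses neither.

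Two contrasts inside the documents make the gap visible:

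- Type 1 and type 2 diabetes are excluded at entry, which helps to keep the gestational diabetes component new-onset. Hypertension has no matching protection up to 160/110.
- SAP 4.2 defines Cesarean delivery, size for gestational age and preterm birth in detail, but gives no rule for separating hypertension present at entry from hypertension that develops later.

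At stake is how one exploratory component, and the composite that contains it, can be read.

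**Working it through.** The plan gives no rate for high blood pressure at entry or for gestational hypertension/preeclampsia, so it has no figure of its own to reproduce here. All rates below are assumptions.

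**1. Who can enter.** The exclusion applies above 160 or above 110. The lower alert tier starts at 140 or 90. The overlap, eligible and high by the protocol's rule, is 140–160 systolic or 90–110 diastolic.

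**2. Does leaving out entry pressure bias the comparison?** Simulation: 330 women, 1:1, 15% control event rate, 2%, 5% or 10% with high pressure at entry, logistic model with and without an indicator for it, 1,500 runs per setting. With no true effect the median unadjusted odds ratio was 1.00 in every setting. Type I error was 3.9–5.4% unadjusted and 4.1–5.7% adjusted. There is no bias.

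**3. Power if high entry pressure is only a risk factor.** Same simulation, true odds ratio 0.5, high entry pressure multiplying the odds of an event by 6:

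| High at entry | OR unadjusted / adjusted | Power unadjusted / adjusted |
|---|---|---|
| 2% | 0.504 / 0.495 | 0.487 / 0.495 |
| 5% | 0.519 / 0.501 | 0.499 / 0.512 |
| 10% | 0.525 / 0.491 | 0.517 / 0.559 |

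A second simulation used a continuous baseline pressure, 140 women per arm (330 × 0.85 ≈ 280 in total), treatment odds ratio 0.4 and 1,500 runs per cell. Entries are power unadjusted / adjusted:

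| Event rate | OR 1.5 per SD | OR 2.0 per SD | OR 2.5 per SD |
|---|---|---|---|
| 10% | 0.43 / 0.42 | 0.42 / 0.43 | 0.41 / 0.43 |
| 15% | 0.59 / 0.60 | 0.56 / 0.60 | 0.51 / 0.56 |
| 20% | 0.72 / 0.74 | 0.71 / 0.72 | 0.67 / 0.72 |

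The change runs from −1 to +5 points. Differences of 1–2 points are close to simulation noise: the standard error of one power estimate near 0.5 is √(0.25/1500) ≈ 1.3 points.

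**4. Dilution if high entry pressure is recorded as the outcome.** Let f be the share high at entry and q the share of those recorded as events in either arm. Assume event rates of 12% (Usual Care) and 8% (SmartMoms) in the other women, a relative risk of 0.67. Then

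RR = [fq + (1 − f) × 0.08] / [fq + (1 − f) × 0.12]

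- q = 0, any f: 0.08/0.12 = 0.67, no dilution.
- f = 0.02, q = 0.5: 0.0884/0.1276 = 0.69; entry cases are 0.01/0.1276 = 8% of Usual Care events.
- f = 0.06, q = 1: 0.1352/0.1728 = 0.78; entry cases are 0.06/0.1728 = 35%.

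On the odds-ratio scale, take 15% control risk and true OR 0.5, so the SmartMoms risk is 0.0882/1.0882 = 0.0811. With 95% of entry cases recorded whatever the arm, each risk becomes p + 0.95f(1 − p):

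| f | Usual Care risk | SmartMoms risk | OR by formula | OR simulated | Power unadjusted / adjusted |
|---|---|---|---|---|---|
| 2% | 0.166 | 0.099 | 0.549 | 0.535 | 0.459 / 0.499 |
| 5% | 0.190 | 0.125 | 0.606 | 0.586 | 0.394 / 0.479 |
| 10% | 0.231 | 0.168 | 0.675 | 0.683 | 0.286 / 0.431 |

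The adjusted odds ratio was 0.49–0.51. Between 5% and 13% of these runs were dropped because a model could not be fitted. The indicator also identified the recorded entry cases almost perfectly, so a real blood-pressure term should be expected to recover less.

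**5. Composite.** No figure was computed. Gestational diabetes and Cesarean events also make it positive, so its dilution would differ.

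**The case against.** A reader might infer that high pressure at entry is in fact counted in the outcome. The documents do not support that. The outcome is a recorded diagnosis, not a study reading, and nothing shows how the birth record treats hypertension that predates randomization. The true q could be near zero. This stands, and it is why the dilution is only conditional.

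A reader might also infer that the missing covariate biases the treatment comparison. It does not, as step 2 shows; a chance imbalance is already reflected in the confidence interval. Nor does a covariate turn a pre-existing condition into a new one. Only the sensitivity analysis addresses that.

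Two further claims have no basis in the documents: that events in women high at entry could not be prevented by the program, and that blood pressure is the strongest baseline predictor. Neither is relied on here.

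Other fair points:

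- The Protocol describes the women as healthy and mentions a pregnancy exercise-readiness screen (11.1), so few may enter with high pressure.
- One reading is not a diagnosis, and Protocol 10.1 allows that some readings were taken under non-standard conditions.
- The silence of SAP 2.1 on blood pressure is weak evidence. That list also omits the smartphone and gestational-age criteria and is evidently abbreviated.
- The comparison is weak in any case. At 12% against 8% with 140 per arm, z = 0.04/√[(0.1056 + 0.0736)/140] = 1.12, which gives power of about 0.2.
- The results are exploratory, and the SAP's note on Section 3.3 says that other covariates will be explored.

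These points keep the matter minor. They do not settle it: the general caution and the general line on other covariates neither name blood pressure nor set apart women who were high at entry.

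**Conclusion.** This is a minor point that holds within limits. Women in the 140–160 or 90–110 range can be randomized, and two exploratory models leave out a baseline value that the trial collects. The comparison stays unbiased. Adjusting would change power by about −1 to +5 points, under assumed event rates of 10–20% and odds ratios of 1.5–2.5 per SD of baseline pressure.

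Dilution arises only if pressure already high at entry is recorded as the outcome, and its size rests wholly on assumed rates. A relative risk of 0.67 would become 0.69–0.78 with 2–6% high at entry and half to all of them recorded, and would stay at 0.67 if none were. As written, the plan cannot say whether a result on this component concerns new-onset hypertension. The primary endpoint and Hypotheses 1 and 2 are not affected.

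**What to change.** In the exploratory part of SAP 4.3, for gestational hypertension/preeclampsia and for the maternal composite only:

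1. Add baseline mean arterial pressure, (systolic + 2 × diastolic)/3, as a single covariate. Use V1, or S1 if V1 is missing.
2. Add one sensitivity analysis that repeats both models without women at 140/90 or above (either component) at S1 or V1. State in advance how repeat readings count; the repeat-reading rule in Protocol 11.2.3 could be reused. This brings the result closer to an effect on new-onset hypertension. It would not remove women with known hypertension whose entry readings were below 140/90.

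The cost is a few lines of SAP text and one more parameter where events may be few; no new data are needed. Readings taken under non-standard conditions will add noise to the covariate and to the 140/90 split. Eligibility, the alert rules and the primary endpoint stay as they are.

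Separately, the Protocol and SAP criteria lists should be reconciled on blood pressure. So should Protocol 5.3 and 11.2.3, since a reading of exactly 160/110 is both eligible and at the upper alert level.
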